### **10.2. Deaths, Serious Adverse Events and Other Significant Adverse Events**

#### **10.2.1. Deaths**

Fatal TEAEs, regardless of causality, will be presented in a by-subject listing.

#### **10.2.2. Serious Adverse Events**

Treatment-emergent serious AEs will be presented in a by-subject listing.

### **10.2.3. Adverse Events Leading to Withdrawal from the Study**

Treatment-emergent AEs leading to withdrawal will be presented in a by-subject listing.

### **10.2.4. Adverse Events Leading to Discontinuation of Study Drug**

Treatment-emergent AEs leading to discontinuation of study drug will be presented in a by-subject listing.

## **10.3. Other Safety Variables**

All safety variables are listed in Section 5.4. [REDACTED]

Categorical safety variables will be summarized descriptively using counts and percentages for each treatment group at each visit.

For continuous safety variables, observed values and change from baseline will be summarized descriptively for each parameter (as appropriate) by treatment group at each visit.

For safety endpoints that assess each eye separately, summaries will be created for the study eye and the fellow eye.

[REDACTED]

[REDACTED]

[REDACTED]

[REDACTED]

[REDACTED]

[REDACTED]

[REDACTED]

[REDACTED]

[REDACTED]

[REDACTED]

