- **Intraocular pressure.** All IOP measurements must be measured by Goldmann applanation or Tono-Pen tonometry as per the investigator's standard clinical practice. To minimize

confounding variables, every effort should be made to measure all IOP measurements for each subject by the same examiner using the same tonometer and approximately at the same time at all visits

- **Fundus examination.** A dilated fundus exam (using 1 drop of tropicamide 1%) consisting of the vitreous, optic nerve, macula, and peripheral retina will be conducted, and the structures will be graded as normal or abnormal
- 
- **Pharmacokinetic assessment.** Blood will be collected and sent for analysis (C_{max} , T_{max} , AUC) of single-dose and repeated-dose INV-102. A blood sample will be collected pre-dose and 5, 15, 30, 60, and 120 minutes post-dose. 
 Refer to the SRM for details on collecting and processing blood samples
- **Adverse events.** The subject will be queried for AEs at each study visit and all AEs will be recorded in the eCRFs, including severity, action taken, and relationship to the study drug

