10.3.4 SAFETY ANALYSES

All safety analyses will be conducted on the safety population using the following safety variables in Parts 1 and 2, unless as described below:

- Treatment-emergent AEs
- Vital signs
- Best-corrected visual acuity
- Slit lamp examination findings
- [REDACTED]
- Intraocular pressure (Part 1 only)
- Fundus examination (Part 1 only)
- Pachymetry (Part 1 only)
- Endothelial cell count (Part 1 only)
- Corneal fluorescein staining (Part 1 only)
- [REDACTED]

- [REDACTED]
- [REDACTED]
- [REDACTED]

Adverse events will be coded using the Medical Dictionary for Regulatory Activities (MedDRA; version 24.1). For each TEAE reported, the number and percent of subjects will be tabulated based on the preferred term. The tables will be generated by relationship to study drug as well as by system organ class and severity. Serious TEAEs and TEAEs leading to discontinuation of study drug and of study will also be summarized. Treatment-emergent AEs will be summarized; any AEs occurring after ICF signing but before initiation of study drug dosing will be presented in the listings but will not be summarized in tables.

Other safety endpoints will be summarized descriptively at each visit, showing actual values and change from Baseline values, where appropriate.

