#### **3.3. Deviations from Study Protocol**

A PK population was added to the set of analysis populations. [REDACTED]  
[REDACTED] Otherwise, the SAP is consistent with the methods described in the study protocol.

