14.3.1.6.1	Treatment-Emergent Adverse Events (TEAE) by System Organ Class, Preferred Term, and Relationship to Study Treatment – Part 1		X			
14.3.1.6.2	Treatment-Emergent Adverse Events (TEAE) by System Organ Class,		X			

Table	Description of Table	All	Safety	mITT	PP	PK
	Preferred Term, and Relationship to Study Treatment – Part 2					
14.3.2.1	Listing of Fatal Treatment-Emergent Adverse Events (TEAE)		X			
14.3.2.2	Listing of Serious Treatment-Emergent Adverse Events (TEAE)		X			
14.3.2.3	Listing of Treatment-Emergent Adverse Events (TEAE) Leading to Withdrawal From the Study		X			
14.3.2.4	Listing of Treatment-Emergent Adverse Events (TEAE) Leading to Study Drug Discontinuation		X			
14.3.3.1	Vital Signs by Visit – Part 1		X			
14.3.3.2	Vital Signs by Visit – Part 2		X			
14.3.4.1	Best Corrected Visual Acuity (logMAR) by Visit – Part 1		X			
14.3.4.2	Best Corrected Visual Acuity (logMAR) by Visit – Part 2		X			
14.3.5.1	Slit Lamp Examination by Visit – Part 1		X			
14.3.5.2	Slit Lamp Examination by Visit – Part 2		X			
14.3.7.1	Intraocular Pressure (mmHg) by Visit – Part 1		X			
14.3.8.1	Fundus Examination by Visit – Part 1		X			
14.3.9.1	Pachymetry (um) by Visit – Part 1		X			
14.3.10.1	Endothelial Cell Count (cells/mm  ) by Visit – Part 1		X			
14.4.2.1	INV-102 Plasma Concentrations (ng/mL) by Visit and Time Point – Part 1					X

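### The visible SAP 10.3 plans no change-from-Baseline summary for slit lamp and fundus findings, so when some eyes are abnormal at Baseline its summary tables cannot separate new from pre-existing abnormalities

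*SAP*

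**What the plan says.** SAP 10.3 gives two rules in adjacent sentences. For categorical measures: "Categorical safety variables will be summarized descriptively using counts and percentages for each treatment group at each visit". For continuous measures: "For continuous safety variables, observed values and change from baseline will be summarized descriptively". For measures taken on each eye, "summaries will be created for the study eye and the fellow eye".

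The planned tables in SAP 14.1 include "Slit Lamp Examination by Visit – Part 1", a matching Part 2 slit lamp table, and "Fundus Examination by Visit – Part 1". No shift table is visible in that list.

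Protocol 9.1 makes the fundus result binary: "the structures will be graded as normal or abnormal". It also requires every slit lamp observation to be recorded, although its grading detail is redacted.

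Protocol 10.3.4 sets the parent rule: "Other safety endpoints will be summarized descriptively at each visit, showing actual values and change from Baseline values, where appropriate". SAP 3.3 declares an added PK population, followed by redacted text, and then says: "Otherwise, the SAP is consistent with the methods described in the study protocol".

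**The concern.** The protocol's rule covers all other safety endpoints. For a categorical examination, the natural form of change from Baseline is a shift from the Baseline category to the later one. The visible SAP keeps change from Baseline for continuous variables and gives categorical ones only a count at each visit, without declaring a departure from the protocol.

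This matters because every subject has moderate dry eye, and the protocol (3.1) chose this population because the eyes are at least partly compromised. Some lid, conjunctival or corneal findings at Baseline are therefore plausible. In a per-visit count, a finding that appears in one eye is offset by a finding that resolves in another, and the table looks flat. The primary objective of Part 1 is to characterize the safety of a first-in-human eyedrop, so a scheduled examination should yield a rate of new findings that can be compared with vehicle.

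The eye-level split adds a second gap. Both eyes are dosed in Part 1, but separate Study Eye and Fellow Eye tables do not show how many subjects had a new finding in at least one dosed eye.

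**Working it through.** The plan states no figure on this point, so there is nothing to reproduce. The check asks what per-visit counts can and cannot reveal.

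**Inputs from the documents.** About 6 active and 3 vehicle subjects per Part 1 cohort (SAP 6). Vehicle is pooled over Cohorts 1 to 4 (SAP 7.4.1): 4 × 3 = 12. Part 2 has about 32 active and 16 vehicle subjects. After Baseline, the slit lamp examination is done at Days 8, 15 and 22 in both parts, and the fundus examination at the same visits in Part 1 (schedules of activities).

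**Assumed.** All abnormality counts below are illustrative, because the documents give no rates. Every eye is taken to have both readings.

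**Formula.** With n eyes (one per subject), b abnormal at Baseline and p abnormal at a later visit, the number newly abnormal lies between max(0, p − b) and min(p, n − b).

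| Group | n | b | p | Newly abnormal |
|---|---|---|---|---|
| Part 1 active cohort | 6 | 0 | 1 | exactly 1 |
| Part 1 active cohort | 6 | 1 | 1 | 0 to 1 |
| Part 1 active cohort | 6 | 2 | 3 | 1 to 3 |
| Part 1 active cohort | 6 | 3 | 3 | 0 to 3 |
| Part 1 pooled vehicle | 12 | 6 | 6 | 0 to 6 |
| Part 2 active | 32 | 8 | 8 | 0 to 8 |

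The fourth row in full: max(0, 3 − 3) = 0 and min(3, 6 − 3) = 3. Of the 6 − 3 = 3 eyes normal at Baseline, anywhere from none to all could be newly abnormal.

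**Comparison with vehicle.** Take 3/6 active and 6/12 vehicle abnormal at both visits. The table shows 50% in each group at each visit. The same table is compatible with new findings in 3 of 3 normal active eyes and 0 of 6 normal vehicle eyes, and with the reverse (0 of 3 and 6 of 6).

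**Per-subject count.** Suppose 2 of 6 subjects have a new finding in the Study Eye and 2 of 6 in the Fellow Eye. The number with a new finding in either eye lies between max(2, 2) = 2 and min(6, 2 + 2) = 4, that is 33% to 67%.

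**Where the problem vanishes.** If b = 0, the later count is exactly the number newly abnormal, as in the first row. This may well be close to the truth for fundus, since dry eye gives no reason to expect abnormal vitreous, optic nerve, macula or retina.

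**The case against.** A reader might infer that new abnormalities cannot be identified in this trial at all. The documents do not support that. SAP 10 puts all safety data into by-subject listings, and listings 16.2.10 (slit lamp) and 16.2.13 (fundus) are planned. With about 6 active subjects per Part 1 cohort, each eye can be followed by hand. In addition, protocol 9.2.4 makes deterioration of a pre-existing condition an AE, and SAP 10.1 tabulates AEs that start or worsen after first dose, counting each subject once. A new finding reported as an AE is therefore counted per subject, whichever eye it is in.

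This stands, but only as a partial answer. Listings hold the pairs without giving a group rate. For the seven slit lamp structures named in protocol 9.1, reading Part 1 by hand means 7 × 3 visits × 2 eyes × 36 subjects = 1,512 comparisons. TEAE tables show what was judged and reported as an AE, and the visible text has no rule that every new examination finding must be reported as one.

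A reader might also take the by-visit table titles as confirmation. They confirm nothing, because vital signs, visual acuity, IOP and pachymetry carry the same form of title and are due change from Baseline as continuous variables.

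Parts of SAP 10.3 are redacted and SAP 14.1 lists only main tables, so a shift summary may exist unseen. However, the skipped table number 14.3.6 and listing number 16.2.11 both fall between slit lamp and IOP, where SAP 5.4 has a redacted safety variable. Those gaps do not point to a hidden slit lamp shift table.

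Finally, a reader might infer that these tables drove the Part 2 dose. The documents do not show this. Protocol 5.2 assigns that review to unmasked personnel under a separate plan, and SAP 4.1 describes the Part 2 endpoints as already chosen from Part 1 results.

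**Conclusion.** The point holds as a gap in the planned safety summaries. The visible SAP specifies no Baseline-to-visit summary for slit lamp or fundus findings, although protocol 10.3.4 calls for change from Baseline where appropriate and the visible part of SAP 3.3 declares no departure on this.

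Its size depends on Baseline abnormality, which the documents do not give. With none, nothing is lost. With an assumed half of a 6-subject cohort abnormal at both visits, the number newly abnormal is undetermined between 0 and 3. With an assumed quarter of the Part 2 active arm (8 of 32), it is undetermined between 0 and 8. Slit lamp is the main case and fundus the weaker one. Corneal staining is a separate Part 1 safety variable, so corneal worsening does not rest on slit lamp counts alone.

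What the visible plan lacks is a group-level rate of new examination findings against vehicle, and a per-subject count across dosed eyes. The individual data themselves are available in the listings. The conclusion assumes that the redacted text contains no shift summary.

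**What to change.** Keep the by-visit counts, since the protocol requires actual values at each visit. Add to SAP 10.3, for dosed eyes:

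- a shift summary from Baseline to each post-dose visit, per structure, for slit lamp in Parts 1 and 2 and fundus in Part 1, shown by treatment group for the Study Eye and the Fellow Eye (in Part 2, the Fellow Eye only where it was dosed);
- a row for eyes newly abnormal at any post-dose visit, with eyes normal at Baseline as denominator, and for eyes worse than Baseline where the finding is graded;
- one per-subject row for a new or worse finding in either dosed eye.

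Add the corresponding entries to SAP 14.1. If a redacted part already provides a shift summary, the sponsor need only confirm it.

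The cost is a short SAP text change and a few more tables to program. The Baseline and post-dose examinations are already scheduled, so no new data are needed.

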## **12. PK ANALYSES**

All PK analyses will be conducted using the PK population. All PK analyses will be completed using the actual treatment a subject received. Observed case data will be used; no imputation will be performed for missing PK data.

Analysis of plasma samples for INV-102 concentration determinations will be performed by a central PK laboratory. Plasma concentrations will be summarized by visit and time point using descriptive statistics. For concentrations that are below the LLOQ, the summary will use one-half the LLOQ as the analysis value. Plots of mean INV-102 concentrations by visit and time point will also be presented.

If appropriate, PK assessments ( $C_{\max}$ ,  $T_{\max}$ , AUC) after a single dose and after repeated INV-102 administration will be summarized by visit using descriptive statistics.

All PK data will be presented in by-subject listings. Unscheduled assessments will not be summarized but will be included in the listings.

## 14. APPENDICES

### 14.1. List of Planned Tables

The list of planned tables includes all of the *main* tables to be presented

Table	Description of Table	All	Safety	mITT	PP	PK
14.1.1.1	Subject Disposition – Part 1	X				
14.1.1.2	Subject Disposition – Part 2	X				
14.1.2.x.1	Demographics and Baseline Characteristics – Part 1		X	X	X	X
14.1.2.x.2	Demographics and Baseline Characteristics – Part 2		X	X	X	X
14.1.3.1.1	Ophthalmic Medical and Surgical History – Part 1		X			
14.1.3.1.2	Ophthalmic Medical and Surgical History – Part 2		X			
14.1.3.2.1	General Medical and Surgical History – Part 1		X			
14.1.3.2.2	General Medical and Surgical History – Part 2		X			
14.1.4.1.1	Prior Medications – Part 1		X			
14.1.4.1.2	Prior Medications – Part 2		X			
14.1.4.2.1	Concomitant Medications – Part 1		X			
14.1.4.2.2	Concomitant Medications – Part 2		X			
14.1.5.1	Study Drug Exposure and Compliance – Part 1		X			
14.1.5.2	Study Drug Exposure and Compliance – Part 2		X			

Table	Description of Table	All	Safety	mITT	PP	PK
				X	X	
				X	X	
				X		
				X		
				X		
				X		
				X		
				X		
				X		
				X		
				X		
				X		
				X		
				X		
				X		
				X		

Table	Description of Table	All	Safety	mITT	PP	PK
14.3.1.1.1	Treatment-Emergent Adverse Events (TEAE) by System Organ Class and Preferred Term – Part 1		X			
14.3.1.1.2	Treatment-Emergent Adverse Events (TEAE) by System Organ Class and Preferred Term – Part 2		X			
14.3.1.2.1	Serious Treatment-Emergent Adverse Events (TEAE) by System Organ Class and Preferred Term – Part 1		X			
14.3.1.2.2	Serious Treatment-Emergent Adverse Events (TEAE) by System Organ Class and Preferred Term – Part 2		X			
14.3.1.3.1	Treatment-Emergent Adverse Events (TEAE) Leading to Withdrawal From the Study by System Organ Class and Preferred Term – Part 1		X			
14.3.1.3.2	Treatment-Emergent Adverse Events (TEAE) Leading to Withdrawal From the Study by System Organ Class and Preferred Term – Part 2		X			
14.3.1.4.1	Treatment-Emergent Adverse Events (TEAE) Leading to Study Drug Discontinuation by System Organ Class and Preferred Term – Part 1		X			
14.3.1.4.2	Treatment-Emergent Adverse Events (TEAE) Leading to Study Drug Discontinuation by System Organ Class and Preferred Term – Part 2		X			
14.3.1.5.1	Treatment-Emergent Adverse Events (TEAE) by System Organ Class, Preferred Term, and Severity – Part 1		X			
14.3.1.5.2	Treatment-Emergent Adverse Events (TEAE) by System Organ Class, Preferred Term, and Severity – Part 2		X			
14.3.1.6.1	Treatment-Emergent Adverse Events (TEAE) by System Organ Class, Preferred Term, and Relationship to Study Treatment – Part 1		X			
14.3.1.6.2	Treatment-Emergent Adverse Events (TEAE) by System Organ Class,		X			

Table	Description of Table	All	Safety	mITT	PP	PK
	Preferred Term, and Relationship to Study Treatment – Part 2					
14.3.2.1	Listing of Fatal Treatment-Emergent Adverse Events (TEAE)		X			
14.3.2.2	Listing of Serious Treatment-Emergent Adverse Events (TEAE)		X			
14.3.2.3	Listing of Treatment-Emergent Adverse Events (TEAE) Leading to Withdrawal From the Study		X			
14.3.2.4	Listing of Treatment-Emergent Adverse Events (TEAE) Leading to Study Drug Discontinuation		X			
14.3.3.1	Vital Signs by Visit – Part 1		X			
14.3.3.2	Vital Signs by Visit – Part 2		X			
14.3.4.1	Best Corrected Visual Acuity (logMAR) by Visit – Part 1		X			
14.3.4.2	Best Corrected Visual Acuity (logMAR) by Visit – Part 2		X			
14.3.5.1	Slit Lamp Examination by Visit – Part 1		X			
14.3.5.2	Slit Lamp Examination by Visit – Part 2		X			
14.3.7.1	Intraocular Pressure (mmHg) by Visit – Part 1		X			
14.3.8.1	Fundus Examination by Visit – Part 1		X			
14.3.9.1	Pachymetry (um) by Visit – Part 1		X			
14.3.10.1	Endothelial Cell Count (cells/mm  ) by Visit – Part 1		X			
14.4.2.1	INV-102 Plasma Concentrations (ng/mL) by Visit and Time Point – Part 1					X

## 14.2. List of Planned Listings

Listing	Description of Listing
16.2.1.1	Subject Disposition
16.2.1.2	Eligibility and Randomization
16.2.1.3	Screen Failures
16.2.2	Protocol Deviations
16.2.3	Treatment Assignment and Analysis Populations
16.2.4.1	Demographics
16.2.4.2	General Medical and Surgical History
16.2.4.3	Ophthalmic Medical and Surgical History
16.2.4.4	Prior and Concomitant Medications
16.2.5.1	Study Drug Dispensing
16.2.5.2	Study Drug Administration
16.2.5.3	Study Drug Return
16.2.5.4	Study Drug Exposure and Compliance
16.2.5.5	INV-102 Plasma Concentrations
16.2.6.1	██████ Dry Eye Disease Symptom VAS
16.2.6.2	Eye Dryness and Eye Discomfort Composite Scores
16.2.6.4	Corneal Fluorescein Staining
16.2.7	Adverse Events
16.2.8	Vital Signs
16.2.9	Best Corrected Visual Acuity
16.2.10	Slit Lamp Examination
16.2.12	Intraocular Pressure (IOP)
16.2.13	Fundus Examination
16.2.14	Noncontact Pachymetry
16.2.15	Endothelial Cell Count

Listing	Description of Listing
16.2.16	Urine Pregnancy Test
16.2.17	General Comments

**14.3. List of Planned Figures**

Figure	Description of Figure	All	Safety	mITT	PP	PK
